8.3 Study Analysis

The objective of this clinical study is to evaluate the safety of hair removal and to verify hair removal and permanent hair reduction using the Versa HR 690 nm applicator assessed by hair counts. For this purpose an average of hair count of 2 blinded reviewers will be done at baseline, following treatments, and at follow up visits. In case of a big discrepancy between 2 blinded reviewers, the hair count will be redone by a third blinded evaluator.

An intermediate safety report will be produced based on analysis of data collected post treatment number one of all the enrolled subjects. A Hair Removal report will be produced based on analysis of data collected at the three-month follow-up visit and a Permanent Hair Reduction report based on the analysis of data collected at the six-month follow-up visit will be the final report. The interim reports will not affect the continuation of the study. The study will regardless of the interim report results, be finalized according to this protocol.

The study reports will provide information for use in research & development, and future planned study. All statistical tests will be two-sided. The level of statistical significance for effectiveness analyses is five percent for all tests of differences. Paired t-test and/or Wilcoxon signed rank test will be used to compare the evaluations at the baseline and follow up sessions. Descriptive statistics and correlations between variables will be performed.

Safety: Adverse events reported will be listed, documenting course, outcome, severity, and possible relationship to the treatment.

9 Adverse Events

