3.1 Primary Objectives

- To evaluate the safety of hair removal using the Versa HR690 nm applicator.
- To verify hair removal and permanent hair reduction using the Versa HR 690 nm applicator, assessed by hair counts.

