4.1 Primary Effectiveness Endpoints

- Hair count reduction, as calculated from photographs and defined as (count-baseline)/baseline*100; 3 months following the last treatment FU2 (hair removal).

- Hair count reduction, as calculated from photographs and defined as (count-baseline)/baseline*100; 6 months following the last treatment FU 3 (permanent hair reduction).

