8.1 Study Hypothesis

The study will confirm that the Versa HR 690 nm applicator is safe for removal of unwanted hair, and will result in hair removal and permanent hair count reduction for patients with Fitzpatrick Skin Type V-VI.

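### Do the open choice of test and the unwritten rule for the two primary endpoints in section 8.3 put the 5% error rate at risk?

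*Combined protocol and SAP*

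**What the plan says.** Section 8.3 sets the level per test: "The level of statistical significance for effectiveness analyses is five percent for all tests of differences". Tests are two-sided, and on method the section says "Paired t-test and/or Wilcoxon signed rank test will be used to compare the evaluations at the baseline and follow up sessions". It gives no overall error rate, testing order or split of the 5%.

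Section 4.1 has two primary effectiveness endpoints, each a percent change from baseline: three months after the last treatment (FU2), labelled hair removal, and six months after it (FU3), labelled permanent hair reduction. Section 8.3 reports them separately: "A Hair Removal report will be produced based on analysis of data collected at the three-month follow-up visit". The FU3 counts go into a second, closing report of their own. The primary objective in section 3.1 joins the two: "To verify hair removal and permanent hair reduction using the Versa HR 690 nm applicator, assessed by hair counts". So does section 8.1, which expects that the applicator "will result in hair removal and permanent hair count reduction for patients with Fitzpatrick Skin Type V-VI".

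The one-month count (FU1) is secondary in the synopsis and in section 4.2. A footnote to Appendix I places it in the Hair Removal report beside FU2.

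**The concern.** Two decisions appear to be left until the results are known. If the t-test and the Wilcoxon test fall on opposite sides of 5%, nothing says which one counts. If one visit is significant and the other is not, nothing says whether the study has succeeded. An analyst free to take the better test, and the better visit, would make false claims more often than the nominal 5% suggests. Section 8.2 gives no SD, effect size or power, so the documents alone cannot show that the result will be too clear for this to matter. The FU1 footnote could also be read as letting a one-month result support the hair removal claim.

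**Working it through.** **Inputs.** From 8.3: two-sided 5% per test. From 8.2: 40 subjects in each of three area groups, 3 × 40 = 120. That product is all that can be reproduced, because 8.2 gives no SD, effect or power. The correlation between FU2 and FU3 and the shape of the changes are assumptions.

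**How the figures were obtained.** The two-endpoint rates are exact bivariate normal probabilities. The rest are simulations at n = 120: 200,000 runs per setting without an effect (Monte Carlo error below 0.06 points for a single endpoint), 100,000 with one. A fresh run for this point reproduced the two-endpoint rates and came within about 0.15 points on the two tests.

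**1. Two endpoints, one named test.** There are three possible readings.

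- Two separate claims: each has its own test, with a false-claim rate of 5% (2.5% in the device's favour).
- Both required: the worst case is a large true effect at FU2 and none at FU3. The simulated rate is 4.9 to 5.0%, so the second endpoint adds nothing.
- Either visit may carry one shared claim: the rate is 1 − P(|Z1| < 1.96, |Z2| < 1.96).

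| Assumed FU2/FU3 correlation | Two-sided | Device's favour only |
|---|---|---|
| 0 | 1 − 0.95² = 9.75% | 1 − 0.975² = 4.94% |
| 0.5 | 9.1% | 4.5% |
| 0.7 | 8.3% | 4.2% |
| 0.9 | 7.0% | 3.5% |

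Only the third reading shows an excess, and no section states it. The separate labels and reports point to the first, and the joined wording of 3.1 and 8.1 to the second. The three-month report cannot stop the study (8.3), so early looks add no error.

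**2. Choice of test, one endpoint, no true effect.** P(either) = P(t) + P(Wilcoxon) − P(both), so P(both) follows from the other three columns.

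| Changes | t | Wilcoxon | Either | Both | Either, device's favour |
|---|---|---|---|---|---|
| Normal | 4.93% | 4.92% | 5.86% | 3.99% | 5.86/2 = 2.93% |
| t, 5 df | 4.91% | 5.05% | 6.52% | 3.44% | 6.52/2 = 3.26% |
| t, 3 df | 4.70% | 5.00% | 6.75% | 2.95% | 6.75/2 = 3.38% |

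Halving is valid because these distributions are symmetric. The rate rises only if the better test is picked afterwards. An analyst who asks both tests to agree, which the wording also allows, stays below 5%. If both endpoints are required but the test is picked freely at each, the worst case is 5.8 to 6.0%.

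**3. When the choice could change the answer.** With normal changes, the change detectable with 80% power is (1.96 + 0.84)/√120 = 0.26 SD. There the t-test rejects in 80.0% of trials, Wilcoxon in 78.2% and at least one in 81.5%; the tests disagree in 5.0%. At 0.5 SD they disagree in 0.03%, and at 1 SD in 0.00%.

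**4. Skewed changes.** The endpoint cannot fall below −100% but has no upper limit, so right skew is plausible. Take lognormal ratios of follow-up to baseline count with assumed log-SD s = 0.2, 0.3 and 0.5. With no change in the mean, the t-test rejects in 5.1 to 5.7% of trials, and Wilcoxon in roughly 8.5%, 13% and 29%. The median change in these settings is exp(−s²/2) − 1 = −2.0%, −4.4% and −11.8%, so Wilcoxon is picking up a real fall in the typical subject. The two tests then answer different questions.

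**The case for a change.** The strongest case for a change is that section 8.1 speaks of confirming an effect, that the wording on the tests is open under every reading of the endpoints, and that a few sentences would close both gaps at no cost in subjects or visits. A rule added after the counts are known could look chosen to fit. With skewed changes, moreover, the two tests can part by far more than a point or two.

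Much of this is true. The rule is not written, and step 4 shows that the choice of test is not neutral when the endpoint is skewed.

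The remedy is weaker. It would name a test without saying which, on the ground that either is acceptable; that rests on symmetric distributions only and fails in step 4. It would also leave open whether FU2 and FU3 are tested in order or both required. Testing in order would bar the six-month claim whenever the three-month one fails, a penalty that separately labelled claims do not call for. The FU1 sentence would repeat what the synopsis and sections 4.1, 4.2 and 8.3 already say: FU1 is secondary, and the hair removal endpoint and its report rest on three months. A footnote listing FU1 in a report does not promote it.

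**Conclusion.** No change follows. The gap is real, but an analyst can fill it sensibly from the text: judge each visit on its own claim at 5%, show both tests beside the descriptive statistics that 8.3 already plans, and treat disagreement between them as a borderline result. Under either reading the documents support, the second endpoint adds no error to a claim. What remains is the choice of test: at most about 5.9 to 6.8% instead of 5% two-sided, or 2.9 to 3.4% instead of 2.5% in the device's favour, and only if the better result is picked afterwards. Those figures assume 120 subjects and symmetric changes. Under skew the gap between the tests can be larger, but the simulated cases have an unchanged mean and a median fall of about 2 to 12%, so they concern small effects. For normal changes of 0.5 SD or more, the choice practically never alters the conclusion. The documents do not say how large the change will be, so this last point is conditional.

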9.1 Adverse Events Definitions

In this study, an Adverse Event (AE) is any undesirable clinical occurrence (sign, symptom, illness, or other medical event), that appears or worsens during the clinical study, or requires medical treatment or intervention to a subjects, whether it is considered to be device related or not. If adverse event occur, the first concern will be the safety and welfare of the patient. Appropriate medical intervention will be made.

Any AE or complication reported by the patient or observed by the physician that occur during or after treatment with the device will be recorded in the medical record or source document and on the Case Report Form. The investigator will determine if the AEs are device related or procedure related. This assessment shall include the onset date, resolution date, severity, seriousness, frequency, treatment and outcome.

Each AE should be assessed according to the following criteria:

9.1.1 Severity

Each AE should be assessed for its severity, or the intensity of an event experienced by the subject.

Mild: Awareness of a sign or symptom that does not interfere with the subject's activity or is transient resolved without treatment and has no sequelae.

Moderate: May interfere with the subject's usual activity and require additional intervention and/or treatment, and may have additional sequelae.

Severe: Significant discomfort to the subject and/or interferes with the subject's activity. Additional intervention and or treatment are necessary. Additional sequelae occur. Severe is used to describe the intensity of an event experienced by the subject.

9.1.2 Relationship of AE to the Device

Each AE should be assessed for its relationship to the device or procedure as identified as follows:

Device: This category should be restricted to adverse events directly attributable to Venus Concept

Procedure: A procedure is any activity that supports the usage of the device

Use the following categories for assigning the certainty of the relatedness:

Definitely Related: An AE is definitely related if it is obvious, certain or there is little doubt regarding the relationship.

Possibly Related: An AE is possibly related if it is capable of being related but relatively unlikely.

Not Related: An AE is not related if it is determined that there is no plausible association.

Unknown: Use this term if there is insufficient information to determine if the AE is related to the device or procedure.

9.1.3 Serious Adverse Events

NOTE: The term serious is not synonymous with severity, which may be used to describe the intensity of an event experienced by the subject). An AE that does not meet any of the below criteria will be classified as non-serious.

A serious AE is any event that:

- Results in, or contributes to a death;
- Is immediately life- threatening (injury or illness);
- Results in hospitalization, or prolongs an existing hospitalization;
- Results in permanent impairment of body structure or function, or in persistent or significant disability/incapacity;
- Results in an injury that requires medical intervention to prevent permanent impairment of body structure or function;
- Is a device malfunction or deterioration in the characteristics and/or performance of the device that results in death or serious deterioration in health;
- Is a device malfunction or deterioration in the characteristics and/or performance of the device that, if it were to occur again, could result in death or serious deterioration in health;
- Results in a congenital anomaly or birth defect.
- Is any medically significant injury, event or experience that requires medical/surgical intervention to prevent one of the outcomes listed above;
- Results in end- organ toxicity, including hematological, renal, cardiovascular, hepatic, gastrointestinal, and central nervous system events;

9.1.4 Pre-existing Conditions

A pre-existing condition should not be reported as an adverse event unless there has been a substantial increase in severity or frequency of problems, which has not been attributed to natural history.

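### Section 9.1.4 withholds adverse-event reporting from some worsening of pre-existing conditions that section 9.1 defines as adverse events

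*Combined protocol and SAP*

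**What the plan says.** Section 9.1 sets the general definition. An AE is an undesirable clinical occurrence "that appears or worsens during the clinical study", and it counts "whether it is considered to be device related or not". No degree of worsening is required. The same section sets the capture rule: "Any AE or complication reported by the patient or observed by the physician that occur during or after treatment with the device will be recorded", both in the source record and on the case report form.

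Section 9.1.1 grades severity from mild upwards. Its lowest grade begins "Awareness of a sign or symptom that does not interfere with the" subject's activity, so minor events are meant to be captured.

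Section 9.1.4 sets a different rule for conditions present at entry: "A pre-existing condition should not be reported as an adverse event unless there has been a substantial increase in severity or frequency of problems". The increase must also be one "which has not been attributed to natural history". The section does not define a substantial increase, and it does not say who makes the natural-history attribution.

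The first primary objective in section 3.1 is "To evaluate the safety of hair removal using the Versa HR690 nm applicator". Adverse events are part of the safety endpoint in section 4.3. The safety analysis in section 8.3 is a listing of reported AEs, with no rate, test or threshold.

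**The concern.** The two sections give different answers for the same event, and a site has no rule for choosing between them. Section 9.1 makes AE status independent of cause. Section 9.1.4 brings a judgement about cause forward, so that it decides whether the event is reported as an AE at all.

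The reported AE list is the main evidence for the hypothesis in section 8.1 that the applicator is safe. The study is baseline-controlled and every subject is treated, so no comparison group would suffer the same loss and offset it.

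The clearest example is pre-existing, mild, non-inflammatory pigment change in the treated area. The exclusions in section 5.2.2 do not name it. If it darkens modestly after treatment, the event resembles PIH, one of the anticipated harms in section 9.1.6. That section also extends follow-up when an AE of PIH occurs, and a darkening that was never classed as an AE might not trigger it.

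**Working it through.** The plan states no figure on this point, so the check compares the two rules case by case.

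| Case | Under 9.1 | Under 9.1.4 | Agree? |
|---|---|---|---|
| Pre-existing condition, unchanged | Not an AE | Not reported | Yes |
| Substantial worsening, not attributed to natural history | AE | Reported | Yes |
| Substantial worsening, attributed to natural history | AE | Not reported | No |
| Modest worsening, not attributed to natural history | AE | Not reported | No |
| Modest worsening, attributed to natural history | AE | Not reported | No |
| New event | AE | Rule does not apply | Yes |

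**Direction.** In all three cases of disagreement, 9.1.4 removes an event that 9.1 includes. In no case does it add one. The number of AEs reported under 9.1.4 is therefore at most the number that meet 9.1.

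**Route to the analysis.** Section 8.3 lists AEs that were reported. An event that 9.1.4 keeps from being reported as an AE does not reach that list.

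**Order of judgement.** Section 9.1.2 asks for relationship to device or procedure to be assessed for each AE. The event is thus an AE first and is attributed second. Section 9.1.4 reverses this order for natural history. Section 9.1.2 has no natural-history category: it offers definitely related, possibly related, not related and unknown. A repair cannot simply pass that attribution to 9.1.2.

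**Who is exposed.** Section 5.2.2 excludes significant concurrent skin conditions, inflammatory skin conditions of any degree, keloid or hypertrophic scars in the treatment area, and sunburn. Section 5.2.1 requires healthy adults. For the treated skin, what remains is mainly mild, non-inflammatory change such as existing pigment variation.

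**Size.** An estimate needs two quantities: the share of subjects who enter with such a condition, and the share of those whose condition worsens modestly or is attributed to natural history. The documents give neither, so no number can be derived.

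**The case against.** Several points on the other side have force.

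- Section 9.1.4 can be read as a specific rule that deliberately narrows a general definition. That reading is available. It still leaves sites with an undefined threshold and no named decider, and 9.1 contains no exception pointing to it.
- A reader might infer that 9.1.4 forbids recording the event, so that the information is lost for good. The text does not go that far: it speaks of reporting as an AE. Treated skin is examined throughout the study and immediate responses are graded after each treatment (sections 7.2.1.1 and 7.2.2.2, Table 1). The whole treatment area is photographed at baseline, before treatments 3 and 6, and at all three follow-up visits (section 7.4.2.1 and Table 1). Visible pigment change would probably leave a trail. That trail is partial, and 8.3 does not plan to use it for the AE listing.
- A reader might infer that pre-existing irritation is a main source of lost events. The exclusion of inflammatory skin conditions plausibly covers it.
- A reader might infer that an unblinded investigator's bias drives the attribution. Section 9.1.4 names no one, and with every subject treated there is no between-arm bias to introduce.
- Section 9.1.6 requires every anticipated AE to be reported. This protects new blistering, burns, infection, scarring and PIH. It does not clearly protect a worsening of existing pigment change, because 9.1.4 governs whether that worsening counts as an AE.

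**Conclusion.** The conflict between 9.1 and 9.1.4 is real and rests on the wording alone. A worsening that is not substantial, or that is attributed to natural history, is an AE under one section and is not to be reported as one under the other. Any effect on the safety listing can only reduce it, and safety is a primary objective in a study with no control arm.

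The size cannot be estimated from the documents. It is probably small, given the exclusions and given that new device-type events are outside the rule. A reader might infer that the safety result is biased or that events are being undercounted to a known extent. The documents do not support that: they show a one-directional inconsistency, not a demonstrated loss. Nor is there a safety threshold that a few missing events could cross. The correction is still worth making, because it replaces a stated rule that works against the plan's own definition and costs very little.

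**What to change.** Align 9.1.4 with 9.1, for example:

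> A pre-existing condition that is unchanged from Visit 0 is not an AE. Any worsening from its Visit 0 status is recorded and reported as an AE. Its relationship to device or procedure is then assessed under 9.1.2. Suspected natural history is noted as a comment on the AE form and is not used to withhold the event.

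The wording should cover worsening anywhere on the body, as 9.1 does, and not only in the treated area. The Visit 0 history, examination and photographs in Appendix I already supply a reference state.

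If the sponsor prefers to keep a threshold, 9.1 should carry the exception explicitly, the threshold should be defined, and the person who decides on natural history should be named. That is the weaker option, since it still places attribution before reporting.

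The cost is a short amendment, with the ethics approval that section 10.10 requires, and a few more mild AEs in the listing.

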9.1.5 Diagnosis of Adverse Event

There should be an attempt to report a "diagnosis" rather than the individual signs, symptoms and abnormal laboratory values associated with the diagnosis. However, a diagnosis should be reported only if, in the Investigator's judgment, it is relatively certain (i.e., definite or possible). Otherwise individual signs, symptoms and abnormal laboratory values should be reported as the adverse events.

9.1.6 Anticipated Outcome Related Adverse Events

Anticipated adverse events in this study may include: blistering, burns, excessive edema or erythema (excessive considered as edema or erythema that do not resolve within 2-3 days), infection, PIH and scarring.

Any anticipated AE that occurs at any time during or after the use of the study device must be reported by the Investigator to Venus Concept. If the anticipated AE, in the opinion of Venus Concept or the Investigator, is likely to affect the safety of the subjects or the conduct of the study, the IRB/ Helsinki/ other ethic committee will be notified of the effect within 10 working days after Venus Concept first receives notice of it. In this study if an adverse event of PIH occurs the Investigator will continue following the subject until the PIH is resolved or up to 6 months following the last visit, whichever comes first.

9.1.7 Unanticipated Adverse Device Effects

An unanticipated adverse device effect as defined by the Federal Regulations [21 CFR 812.3(s)] is “any serious adverse effect on health or safety or any life-threatening problem or death caused by, or associated with, a device, if that effect, problem, or death was not previously identified in nature, severity, or degree of incidence in the investigational plan or application (including a supplementary plan or application), or any other unanticipated serious problem associated with a device that relates to the rights, safety, or welfare of subjects.” From a practical perspective, an unanticipated adverse device effect means a serious adverse event that is not listed in the device labeling, or the frequency or severity is greater than reported in the device labeling.

In the event of a serious (or unanticipated) adverse event, the Investigator will immediately notify the Venus Concept monitor by telephone. If such an adverse event is being reported after normal working hours, the Investigator will leave a voice message with accompanying report of the AE.

